6.4.2.2 ColorFace®

The ColorFace® acquisition system is a dedicated solution developed by Newtone Technologies for standardized imaging in the clinical study setting for evaluation of a clinical effect [20]. This innovative solution is based on a high-resolution sensor to obtain high-quality standardized images (24M pixel sensor). In addition, specific lighting allows multimodal captures in cross polarization, parallel polarization, standard lighting and ultraviolet for analysis.

The ColorFace® ensures reliable and reproducible repositioning of subjects over time, thanks to an ear support coupled with a control of the head tilt and by a real-time visualization by the operator. Without chin strap or retention system on the forehead, it allows full exploitation of the face.

Three pictures of subject's face at rest (1 front face picture and 2 profiles 45° pictures) will be taken at D0 and at each time point after the baseline (D15, D36 and D57 before the MD application).

NB:

For pores analysis: front face image and PP polarization

For texture analysis: profiles images and CP and Std 60 polarization

6.4.2.3 Pores and texture analysis by NEWTONE

After thorough quality control of the images, the images will be analyzed with a focus to pores (in parallel polarized light in front views) and cheek (or other relevant area) texture (in cross-polarized (CP) light profile views or standard 60 light (std60) profile views).

Pores analysis will provide parameters of the pores visibility (conspicuous surface, length, volume, density of pores, and average surface of detected pores) and will enable conclusion on the evolution of these elements overtime under the effect of the treatment.

Texture will be analyzed either with a colorial texture analysis (in CP images) or the line marks approach (in std60 images).

- Colorial texture is an approach to apprehend the evolution of the skin contrasts and pixels luminosity organization evolution overtime, and possible consequence on the perception of the skin surface roughness. Colorial contrast and entropy parameters will be delivered. To reveal texture and roughness evolution of the skin this analysis should be performed in skin areas where the colour organization does not evolve significantly.
- Line marks analysis is an approach to apprehend the detection and followup of small oriented surface elements that contribute to the skin roughness perception. Parameters related to these elements visibility will be provided. To reveal texture of and roughness evolution overtime, this analysis should be performed in skin areas where the colour organization does not evolve significantly. Gloss evolution may also impact this analysis and will be taken into account to the choice of the approach.

One or the other of these approaches will be used depending of the images received.

The region of interest will also be defined as regards analysis relevance in the context of the study endpoint.

6.4.2.4 Investigator Global Assessment

The investigator (the second evaluator not performing the peeling act) will evaluate the global effect of the medical device on D78.

				
Worse	No improvement	Slight improvement	Good improvement	Very good improvement
-1	0	1	2	3

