6.4.1.1 Staff involved in the study

There will be three different kinds of personnel involved in the study:

- Investigators performing the peeling act (qualified practitioners): they will oversee the inclusions of subjects and they will be in charge of the device application;
- Live independent evaluators (investigators): the follow-up of subject's and the scoring in live.
- Technicians: operators: they will oversee the photographs taking .

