6.4.2.5 Patient Global Assessment

The subject will evaluate the global effect of the medical device on D78.

				
Worse	No improvement	Slight improvement	Good improvement	Very good improvement
-1	0	1	2	3

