7.2.2 Secondary endpoint(s)

- Pores and texture analysis (will be performed by Newtone with Colorface acquisitions)
- Visual effect (Standardized anonymized photographs (face, 45° at left, 45° right) with Colorface)
- Investigator Global Assessment
- Patient Global Assessment
- Local and overall tolerance of the Crystal Peel, a salicylic acid-based peel, used under the normal conditions of use recommended by the manufacturer.
- Subject's self-evaluation on D78 using a questionnaire.
- Potential adverse events collection.

Analysis of primary and secondary endpoints 'parameters':

For each continuous variable obtained from devices: A mixed linear model for repeated measurements (PROC MIXED) will be fitted to raw data.

Using the adjusted means obtained from this model (LS-Means), the contrast of interest will be built:

- To assess the change from first measurement at each time

The underlying assumptions (normality and homoscedasticity of residuals) will be checked using Shapiro-Wilk test ($\alpha=0.01$) and graphical representations.

In case of strong deviation, a transformation of the data or a non-parametric approach (Wilcoxon signed rank tests) will be performed.

The raw score will be summarized using descriptive statistics for quantitative data by time point. A Wilcoxon signed rank test will be applied to test whether the change from baseline is statistically significant.

The categorical data will be summarized in frequency (N) and percentage (%) associated with its 95% confidence interval by time point.

The questionnaire will be summarized in frequency (N) and percentage (%).

The adverse events will be analysed.

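### The IGA and PGA scales cap worsening at −1 but grade improvement up to +3, and the D78 rating has no stated reference; analysed as scores, these secondary endpoints lean towards benefit

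*Combined protocol and SAP*

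**What the plan says.** Sections 6.4.2.4 (IGA) and 6.4.2.5 (PGA) print the same five boxes. The lowest, for worsening, is coded −1 and the next, for no improvement, is coded 0. The third, and so the middle of the row, is "Slight improvement" at +1. Good improvement is +2, and the top box, "Very good improvement", is +3.

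The IGA instruction is "The investigator (the second evaluator not performing the peeling act) will evaluate the global effect of the medical device on D78". The PGA instruction is "The subject will evaluate the global effect of the medical device on D78". The flow-chart in section 6.1.4 and the schedule in section 6.4.1.2 place both ratings at D78 only.

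Baseline material exists. Section 6.4.2.2 states that "Three pictures of subject's face at rest (1 front face picture and 2 profiles 45° pictures) will be taken at D0", and lesions are counted at D0 as well. Section 6.4.1.1 gives the independent evaluators "the follow-up of subject's and the scoring in live". No section says that the D0 photographs or counts are put before the second evaluator or the subject at D78.

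On analysis, section 7.2.2 has one rule for scores, "The raw score will be summarized using descriptive statistics for quantitative data by time point" followed by "A Wilcoxon signed rank test will be applied to test whether the change from baseline is statistically significant", and another for categorical data (N, % and 95% confidence interval). It assigns the IGA and PGA to neither. The synopsis and section 6.1.3.2 list both as scores.

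**The concern.** The two directions of change are measured with different rulers. A slight deterioration and a marked one both score −1, while improvement can earn one, two or three points. Any summary that uses the size of the codes therefore gives more weight to improvement than to worsening.

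The question also asks for an effect of the device, not for a change from a named starting point, so two raters could answer it against different references.

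Both features matter more here than they would in a controlled trial. The study is open, single-centre and without randomisation (sections 6.1.1 and 6.3.6), and bias management is marked not applicable (sections 6.1.2 and 7.7). No comparison group exists in which the same upward shift would appear and cancel. At stake is how far the two global efficacy ratings can be read as support for the lesion-count result.

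**Working it through.** The plan gives no expected mean, SD, power or threshold for the IGA or PGA, so there is no figure of its own to reproduce.

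**Inputs.** Codes −1, 0, 1, 2, 3 (sections 6.4.2.4 and 6.4.2.5). N = 30 evaluable (section 6.1.6). Two-sided 5% level (section 7.3). Because no D0 rating exists, the signed-rank test of change from baseline has no baseline value to subtract. I take it as a test of the D78 score against 0; this is an assumption.

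**Step 1: a worked case on the plan's scale.** Let 16 subjects be worse (−1) and 14 score +2.
- Mean = (−16 + 28)/30 = +0.40. Median = −1.
- Ranks of absolute values: the 16 values of size 1 share rank (1 + 16)/2 = 8.5, and the 14 values of size 2 share rank (17 + 30)/2 = 23.5.
- W− = 16 × 8.5 = 136. W+ = 14 × 23.5 = 329. Expected value = 30 × 31/4 = 232.5.
- Tie-corrected variance = 30 × 31 × 61/24 − [(16³ − 16) + (14³ − 14)]/48 = 2363.75 − 141.875 = 2221.875; SD = 47.14.
- z = (329 − 232.5)/47.14 = 2.05, two-sided p = 0.041 (exact sign-flip p = 0.035), in the direction of improvement with 16/30 = 53% worse.

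A worsening can never outrank a +2 or +3, however marked it was.

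**Step 2: isolate the cap.** Keep the same 14 at +2, but suppose the 16 worsenings differed in degree and could be graded −1 (6 subjects), −2 (5) and −3 (5). This split is assumed for illustration.
- Mean = (−6 − 10 − 15 + 28)/30 = −0.10.
- Shared ranks are 3.5 for size 1 (6 values), 16 for size 2 (19 values) and 28 for size 3 (5 values). W+ = 14 × 16 = 224; W− = 6 × 3.5 + 5 × 16 + 5 × 28 = 241. z = −0.18, p = 0.86.

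The same subjects move from a significant improvement to no signal once worsening is graded.

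**Step 3: no true change.** Assume that perceived change is normal with mean 0, and that boxes are chosen at cut-points −0.5, 0.5, 1.5 and 2.5. The model, the cut-points and the SDs are assumptions; nothing in the documents fixes them.

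| SD | P(−1) | P(0) | P(+1) | P(+2) | P(+3) | Expected mean |
|---|---|---|---|---|---|---|
| 1 | 0.309 | 0.383 | 0.242 | 0.061 | 0.006 | +0.07 |
| 1.5 | 0.369 | 0.261 | 0.211 | 0.111 | 0.048 | +0.21 |
| 2 | 0.401 | 0.197 | 0.175 | 0.121 | 0.106 | +0.33 |

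For SD 1: −0.309 + 0.242 + 2 × 0.061 + 3 × 0.006 = +0.073. On a scale with mirrored boxes the expected mean is 0 at every SD. Simulating trials of 30 under the same assumptions, the signed-rank test against 0 was significant for improvement in about 5%, 12% and 21% of trials at SD 1, 1.5 and 2, against a nominal 2.5%.

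**The case against.** Several counter-arguments stand.

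- **A mean does not have to be the summary.** Section 7.2.2 leaves the choice open. Under the categorical rule the percentage worse is already reported with its interval. Under the score rule, section 7.2 also asks for the median, which in Step 1 is −1. The bias therefore depends on a score analysis. The name given to the endpoints suggests one but does not settle it. Even the categorical report would not show how marked the worsening was.
- **A positive mean with most subjects worse can occur on a balanced scale too**, if the worsenings are mild and the gains large. A reader might take that result as the defect itself. It is not; the defect is the cap, which Step 2 isolates. The result also needs a particular pattern: with 16 of 30 worse, the other 14 must average above 16/14 = 1.14.
- **A reader might infer that the ratings are made from memory.** The documents do not say so. They name no reference at all, and the evaluators' follow-up role may well involve earlier contact with the subject.
- **A reader might infer that severe flares would be hidden.** At trial level they would not be. Lesions are counted at every visit (section 6.4.2.1), and section 14.3.1 requires a baseline condition that worsens to be recorded and graded for severity. The loss is within these two ratings.
- **The noise model is assumed**, and at SD 1 the shift is small: 0.07 on a scale spanning 4 points.
- **The endpoints are secondary** and have no pass/fail criterion (section 7.5.2), so no stated decision turns on them.

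These limit the reach of the point. They do not answer the asymmetry of the codes or the missing reference, both of which follow from carrying out the plan as written.

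**Conclusion.** The point holds as a recommended improvement to two secondary endpoints. The asymmetry and the absence of a stated reference are plain in sections 6.4.2.4 and 6.4.2.5. The bias towards improvement is conditional on the IGA and PGA being analysed as scores, with the signed-rank test read as a test against 0.

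On that condition, a trial with 53% of subjects worse can show p = 0.041 for improvement. With no true change, the expected mean is +0.07 to +0.33 instead of 0 for assumed rating SDs of 1 to 2. The first figure is a possible result, not a forecast, and the second rests on the assumed noise model. The lesion-count endpoint and the safety data are not affected.

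**What to change.** - Replace both five-box scales with a balanced one that has equal numbers of worsening and improvement grades around no change, for example −3 to +3.
- Word both items as change in facial acne compared with D0, and show the existing D0 photographs to the second evaluator and the subject when they rate at D78.
- State in section 7.2.2 which rule applies to the IGA and PGA. Report the full distribution by box, with exact 95% limits for the percentage improved and the percentage worse, and do not lead with the mean.

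**Cost.** One eCRF page and one subject form change. No visit or acquisition is added, because the photographs are already taken. Results would not be directly comparable with any earlier reports that used the five-box scale. The change has to precede the first D78 rating, since worsening that was not graded then cannot be recovered from these ratings later.

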6.4.2.5 Patient Global Assessment

The subject will evaluate the global effect of the medical device on D78.

				
Worse	No improvement	Slight improvement	Good improvement	Very good improvement
-1	0	1	2	3

6.4.2.6 Subjective questionnaire

Subjects will be asked to complete the satisfaction questionnaire on D78.

6.4.3 **Description of safety parameters**

6.4.3.1 Local tolerance

At the end of the study, the local tolerance on the skin of the product will be assessed during the clinical examination. Abnormal clinical signs and subjective signs reported by the subjects will be reported in the CRF.

According to these signs, the **local tolerance** of the product will be defined on the following scale:

- 0= Bad tolerance
- 1= Moderate tolerance
- 2= Good tolerance
- 3= Very good tolerance.

6.4.3.2 General tolerance

Collection of adverse events by the investigator.

6.4.4 Description of activities performed by sponsor representatives

The sponsor has delegated the following activities to the CRO (Eurofins Dermascan Pharmascan):

- Overall management of the study: document writing, coordination and training of staff participants, study realization and inclusions status follow-up.
- Submission of the study files to the Ethics Committee (EC) and Competent Authority (CA).
- Management of investigators contracts and fees payment.
- Data management
- Statistical analysis and clinical investigation report writing.

6.4.5 Any known or foreseeable factors that may compromise the outcome of the clinical investigation or the interpretation of results and the methods for addressing these factors

None.

6.4.6 Justification of follow-up period duration

The follow-up period of 78 days shall permit the demonstration of investigational device clinical effectiveness and safety. This period is sufficient to represent a realistic test of the investigational device and allow any risks associated with adverse device effects to be identified and assessed.

6.4.7 Medical care and follow-up to be provided for the subjects after the clinical investigation has been completed

No medical care nor follow-up will be provided after the clinical investigation end (Last Subject Last Visit; see section 6.1.9) unless the subject presents an ongoing adverse device effect or adverse event linked to the CIP procedures at its last visit. In that case, the subject will be followed-up by phone or with a visit to the laboratory until resolution of the adverse event.

6.4.8 Disposition/Future use of samples obtained from subjects

Not applicable. No samples will be taken for this investigation.

6.5 MONITORING PLAN

6.5.1 General outline of the monitoring

The monitoring of the study will be done by Eurofins Dermascan Pharmascan. The Clinical Research Associate (CRA) has the responsibility to familiarise the investigators and the investigation site staff involved in the study with all applicable study Standard Operating Procedures (SOPs). The CRA has the responsibility

DERMOSCIENCES FRANCE	Medical Device CIP # 22E2387	Final version 1.0 Date: 16.08.2022	Confidential Page 33/49
-------------------------	---------------------------------	---------------------------------------	----------------------------

of reviewing the ongoing study with investigators to verify adherence to the CIP and to deal with data queries as well as any problems that arise during the conduct of the study.

A monitoring plan will be written and validated by the sponsor before any monitoring activities can be performed.

6.5.2 Access to source data

In accordance with good clinical practices and the standards of the data protection law, data obtained during a research involving human beings must be treated confidentially to guarantee the subjects' data privacy.

The investigator agrees that, subject to local regulations and ethical considerations, the sponsor representatives' designee and/or and any regulatory agency have direct access to all study records, CRFs, corresponding subject medical records, study drug dispensing records and study drug storage area, and any other documents considered as source documentation. The investigator also agrees to assist the representative, if required.

6.5.3 Extent of source data verification

The monitoring strategy is defined in agreement with the sponsor and depends on several factors to take into consideration during the risk assessment:

- Monitoring type (on-site, a combination of on-site and remote (centralized), or centralized monitoring only).
- Monitoring frequency (early, initial assessment or throughout the study)
- Monitoring extent (100% data verification, targeted or random review of certain data).

The choice of monitoring strategy is also based on the following criteria:

- Study duration
- Number of subjects to randomize, populations of subjects
- Investigational sites (number, subsidiary or not, geography)
- Investigator experience in clinical trials and previous experience with him
- Study design / protocol complexity
- Principal endpoint of the study (subjective/objective, of effectiveness or safety or mixed)
- Type of collected data.

On Sponsor's request, a 100% documents review will be done.

The CRA ensures the coherence and the veracity of the data reported in the CRF compared to the source data and the CIP.

7- STATISTICAL DESIGN AND ANALYSIS

The statistical analysis will be performed by the CRO biostatistician.

The applicable statistical methods will be described, in this CIP section.

7.1 ANALYSIS POPULATION AND PROCEDURES THAT TAKE INTO ACCOUNT ALL THE DATA

The following analysis populations will be studied and will be considered for the statistical analysis:

- Safety population: any subject having used the investigational device.
- ITT (Intent-to-Treat): any subject included and randomized in the study with at least a post-basal value.
- PP population: any subject included and randomized having used at least once the investigational device and without any major deviation to the CIP.

In case the ITT and PP population differ by less than 10%, only the ITT population will be analyzed.

7.2 DESCRIPTIVE STATISTICS AND ANALYTICAL PROCEDURES

The analysis of the effectiveness parameters will be performed on the ITT and PP population. The analysis of the safety/tolerance parameters will be performed on the “safety” population.

The continuous variables will be summarized using the descriptive statistics for quantitative data (number of valid values, number of missing values, means, standard deviations, standard errors of the mean, medians, minimum values and maximum values) for each time.

The categorical data will be summarized in frequency (N) and percentage (%) by time point.

7.2.1 Primary endpoint

Comparison of the change from baseline of total sum of lesions on each visit- objective counting of the lesions by the investigator.

Total lesions will be defined as the sum of inflammatory lesions (papules, pustules), non-inflammatory lesions (whiteheads and blackheads) and other acne lesions (nodules).

7.2.2 Secondary endpoint(s)

- Pores and texture analysis (will be performed by Newtone with Colorface acquisitions)
- Visual effect (Standardized anonymized photographs (face, 45° at left, 45° right) with Colorface)
- Investigator Global Assessment
- Patient Global Assessment
- Local and overall tolerance of the Crystal Peel, a salicylic acid-based peel, used under the normal conditions of use recommended by the manufacturer.
- Subject's self-evaluation on D78 using a questionnaire.
- Potential adverse events collection.

Analysis of primary and secondary endpoints 'parameters':

For each continuous variable obtained from devices: A mixed linear model for repeated measurements (PROC MIXED) will be fitted to raw data.

Using the adjusted means obtained from this model (LS-Means), the contrast of interest will be built:

- To assess the change from first measurement at each time

The underlying assumptions (normality and homoscedasticity of residuals) will be checked using Shapiro-Wilk test ($\alpha=0.01$) and graphical representations.

In case of strong deviation, a transformation of the data or a non-parametric approach (Wilcoxon signed rank tests) will be performed.

The raw score will be summarized using descriptive statistics for quantitative data by time point. A Wilcoxon signed rank test will be applied to test whether the change from baseline is statistically significant.

The categorical data will be summarized in frequency (N) and percentage (%) associated with its 95% confidence interval by time point.

The questionnaire will be summarized in frequency (N) and percentage (%).

The adverse events will be analysed.

7.3 SIGNIFICANCE LEVEL AND POWER OF PRIMARY ENDPOINT(S)

All statistical tests will be assessed at $\alpha = 5\%$ level of significance in a bilateral approach.

DERMOSCIENCES FRANCE	Medical Device CIP # 22E2387	Final version 1.0 Date: 16.08.2022	Confidential Page 35/49
-------------------------	---------------------------------	---------------------------------------	----------------------------

7.4 SAMPLE SIZE AND ITS STATISTICAL JUSTIFICATION

The number of subjects determined is standard for this kind of study and is considered as sufficient to reach the study objectives, and thus, based on previous experiences.

7.5 PASS/FAIL CRITERIA TO BE APPLIED

7.5.1 Primary endpoint

Not applicable

7.5.2 Secondary endpoint(s)

Not applicable

7.6 PROVISION FOR AN INTERIM ANALYSIS AND CRITERIA FOR THE TERMINATION OF THE CLINICAL INVESTIGATION ON STATISTICAL GROUNDS

As no interim statistical analysis has been planned, no statistical criteria for the termination of the clinical investigation have been defined.

7.7 MANAGEMENT OF BIAS

Not applicable.

